#### 8.2.2. Inclusion Criteria

Across all 3 registries, adult patients ( $\geq$ 18 years) of any sex with UC that are enrolled in 1 of the 3 IBD registries after 10 March 2023 and during the observational period (complying with the register's requirements for inclusion including patient consent) and initiated on filgotinib after 10 March 2023. Initiation is defined as either no prior filgotinib use or prior use that was discontinued before 10 March 2023 (thus, patients who are non-naïve to filgotinib can be included).

There are no restrictions on patient inclusion in terms of either historical data or minimum amount of follow-up.

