## 8.5. Study Size

This is a descriptive study without prespecified hypotheses. The goal is to obtain data on up to 500 eligible patients with UC initiating filgotinib during the observational period (per registry) and thus the study size will be dictated by the number of filgotinib patients identified in the participating registries. For illustrative purposes, by applying the rule-of-3 (Hanley & Lippman-Hand, 1983) and assuming an underlying proportion e.g. of a contraindication of 1%, implies that the contraindication would be detected with a certainty of 95% for a sample size of 300 patients; if the underlying proportion of contraindication is 2%, then a sample of 150 patients would suffice (see Table 3).

Underlying Proportion of Contraindication	Sample Size to Detect Contraindication
1%	300
2%	150
3%	100
4%	75
5%	60

 Table 3
 Sample Size Requirements to Detect Contraindication with 95% Certainty

In terms of precision, if the observed proportion of patients at high risk, for example MACE, is 10% among a sample size of 300 users of filgotinib, then this will be estimated with a precision (standard error) of 1.7% resulting in a 95% CI of 6.6% to 13.4% (Altman, 1999). Other scenarios of precision are provided in Table 4 and Figure 2.

Table 4	Standard Error	by Study S	Size and Under	lving Proportion
				J 8

	Study Size				
Proportion*	200	300	400	500	
2%	1.0%	0.8%	0.7%	0.6%	
5%	1.5%	1.3%	1.1%	1.0%	
10%	2.1%	1.7%	1.5%	1.3%	
15%	2.5%	2.1%	1.8%	1.6%	

\* Proportion of patients at high risk of MACE, VTE, or serious and opportunistic infection. Calculations are based on a normal distribution assumption for the proportion

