## 8.7. Data Analysis

Detailed methodology for the analyses of data included in this study will be documented in a common and harmonized statistical analysis plan (SAP), which will be created by the study coordinating center with input from investigators from the 3 registries, dated, filed, and archived by the MAH. Data analysis summarized in the protocol may be modified in the SAP to reflect usage of the most up-to-date methodology used by the different registries.

Data will be summarized using univariable descriptive statistical methods. Categorical outcome variables will be summarized by number and percentage of patients in each categorical definition including 95% CIs. Counts for missing values will be also tabulated but missing values will not be considered in the percentages. Continuous variables will be summarized descriptively (mean, standard deviation, and median, lower quartile, upper quartile, minimum, maximum).

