#### Follow-up

Among women starting filgotinib, the number and proportion who become pregnant during follow-up will be reported. Similarly, the number and proportion of patients who have a new

diagnosis of TB during follow-up, a serious acute infection, a diagnosis of viral hepatitis, concomitant treatment with other immunosuppressants, or who are administered a live attenuated vaccine will be reported. In patients with TB, or a serious infection identified during follow-up, it will be assessed whether treatment was stopped or interrupted after the diagnosis. The proportion of patients who have a test for lipids at around 12 weeks since initiation of filgotinib will be reported.

Should a VTE event occur, subsequent changes to filgotinib use will be reported (filgotinib treatment persistence or discontinuation).

Assessment of the filgotinib maintenance dose during follow-up will also be done in the subgroup of patients at high risk of MACE, VTE, or malignancy. In addition, the average daily dose during the maintenance period and the duration of use during the follow-up period will be reported.

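### Duration of use is summarised by crude mean and median although follow-up is cut off at study end, so it understates treatment duration and depends on recruitment timing

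*Protocol*

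**What the plan says.** Section 7 makes compliance with posology and duration of use an objective. The Follow-up part of Section 8.7 states that "the average daily dose during the maintenance period and the duration of use during the follow-up period will be reported". The method that Section 8.7 gives for continuous data is: "Continuous variables will be summarized descriptively (mean, standard deviation, and median, lower quartile, upper quartile, minimum, maximum". Only univariable descriptive methods are named. No time-to-event method appears.

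Section 8.2.4 starts follow-up at first filgotinib use after the decision date. It ends follow-up at the earliest of discontinuation, withdrawal (including death and loss to follow-up) or end of study. Section 8.1 fixes a 4-year observational period, with an interim report on 2 years of data. Section 8.5 sets the size: "The goal is to obtain data on up to 500 eligible patients with UC initiating filgotinib during the observational period (per registry"). Section 8.2.2 adds, for all three registries: "There are no restrictions on patient inclusion in terms of either historical data or minimum amount of follow-up". Section 8.2.1.2, however, asks that ICC patients be in the registry for at least 12 weeks before analysis.

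On monitoring, Section 8.7 says: "The proportion of patients who have a test for lipids at around 12 weeks since initiation of filgotinib will be reported". Pregnancy, tuberculosis, serious infection, viral hepatitis, concomitant immunosuppressants and live vaccines during follow-up are to be given as numbers and proportions.

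**The concern.** Because follow-up ends at discontinuation or at study end, whichever comes first, the recorded duration is the smaller of the time to stopping and the time to the cut. A patient who starts one month before the cut and stays on treatment enters the mean and median as one month of use.

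The resulting figure mixes how long patients stay on filgotinib with when they happened to start. The interim and final reports could then show different durations under unchanged prescribing, and so could two registries with different uptake curves. A reader comparing them could take the difference for a change in practice.

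**Working it through.** **The plan's own figures.** Section 8.5 gives no figure for duration of use; its calculations concern detection and precision, and they reproduce.
- Rule of three: 3/0.01 = 300, and 1 − 0.99^300 = 0.951. This agrees with "implies that the contraindication would be detected with a certainty of 95% for a sample size of 300 patients".
- Standard error: √(0.10 × 0.90/300) = 1.73%, and 10% ± 1.96 × 1.73% = 6.6% to 13.4%. This agrees with "precision (standard error) of 1.7% resulting in a 95% CI of 6.6% to 13.4"%.

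**Inputs for the duration check.**
- From the Protocol: end of follow-up (8.2.4), a 48-month window with a 24-month interim (8.1), no minimum follow-up (8.2.2), and mean/median summaries (8.7).
- Assumed, because the documents give no value: entry spread evenly over the window, and exponential time to discontinuation T with true median 12 or 24 months.

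**Formulas.** Let λ = ln 2 / true median, let A = 48 (final) or 24 (interim), and let time to the cut C be uniform on (0, A).
- Crude median: the t that solves exp(−λt)(1 − t/A) = 0.5.
- Share still on treatment at the cut: (1 − exp(−λA))/(λA).
- Crude mean: (1/λ) × (1 − share still on treatment).

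Example with true median 24 and A = 48: λ = 0.0289. At t = 13.0, exp(−0.0289 × 13.0) × (1 − 13.0/48) = 0.687 × 0.729 = 0.50. The share still on treatment is (1 − 0.25)/1.386 = 54%.

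| Assumed true median (mean), months | Cut | Crude median | Shortfall in median | Crude mean | Still on treatment | Kaplan-Meier median |
|---|---|---|---|---|---|---|
| 12 (17.3) | final | 8.6 | 28% | 11.5 | 34% | 12.0 |
| 24 (34.6) | final | 13.0 | 46% | 15.9 | 54% | 24.0 |
| 12 (17.3) | interim | 6.5 | 46% | 7.9 | 54% | 12.0 |
| 24 (34.6) | interim | 8.6 | 64% | 9.6 | 72% | not reached |

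The Kaplan-Meier values and a check of the crude values come from simulating 400,000 patients per scenario. Across assumed true medians of 6 to 36 months, the crude median runs from 5.0 to 15.6 months at the final cut and from 4.3 to 9.6 at the interim. It is below the true median in every case.

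**Sensitivity to early closure.** If all patients had entered by month 24, nobody would be cut off before 24 months of follow-up at the final cut. The crude median would then equal the true one for any true median up to 24 months, though the mean would still be shortened.

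**Follow-up events.** Assume a 12-month event risk of 5% and the same even entry, counting administrative cut-off only. Initiators with at least 12 months before the cut contribute 5.0%. Those with less contribute on average 1 − 0.05/0.0513 = 2.5%. The crude proportion with an event in the first 12 months is 0.75 × 5.0% + 0.25 × 2.5% = 4.4% at the final cut, and 0.5 × 5.0% + 0.5 × 2.5% = 3.8% at the interim.

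**The case against.** **The wording is literally accurate.** Duration within the follow-up period is observed exposure, and a mean or median describes that correctly. This stands, but only for that quantity. The objective concerns duration of use as a matter of compliance, so readers will take the figure as treatment duration.

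**The SAP may settle it.** Section 8.7 sends detail to a SAP that may modify the analysis. That is a permission. The Protocol itself fixes the end of follow-up, the absence of a minimum and the form of summary, and together these produce the problem.

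**The size may be smaller.** Entry could close early at 500 patients, and the effect on the median could then vanish. This stands as a limit on the illustration. The only uptake counts in the documents do not point to early closure: Section 8.9 gives 54 ICC and 44 SWIBREG patients for the roughly 16 months from 12 November 2021 to 10 March 2023. That is about 3.4 and 2.8 a month, against 500/48 = 10.4 a month needed to fill the cap by the end. Uptake may of course have changed since.

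**Sweden may err the other way.** Section 8.3.3.3 assumes that each dispensing lasts 180 days. If the actual supply is shorter, recorded duration is lengthened by an unknown amount. That is a separate error and does not correct for censoring.

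**Stronger readings the documents do not support.** A reader might infer that follow-up compliance is biased downward along with duration. It is not so in general: short follow-up misses unwanted events such as live vaccination, so compliance looks better. A reader might also infer that the lipid proportion is taken over all initiators. Section 8.7 fixes no denominator, Table 5 lists lipids as unavailable in SWIBREG, ENEIDA has no chart abstraction at the interim, and the ICC 12-week rule removes most of the cut-off effect there. No shortfall figure for lipid testing is therefore justified. Average maintenance dose is already tied to the maintenance period, and an age limit on the pregnancy denominator is a presentation choice unrelated to censoring.

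**Conclusion.** The point holds for duration of use. Under the stated design, the crude mean and median understate how long patients stay on treatment, and they move with the data cut and the entry pattern. With even entry and exponential persistence, the median falls short by 28% to 46% at the final cut and by 46% to 64% at the interim, for true medians of 12 and 24 months. These sizes are illustrative, since neither the discontinuation rate nor the entry pattern is in the documents. The direction does not depend on the exact rate, as long as some patients are still on treatment when cut off early enough to affect the summary. The Swedish dispensing rule could offset it in that registry.

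Three lesser points stand beside it. Crude proportions of follow-up events ignore unequal follow-up. The Week-12 lipid proportion has no stated at-risk group. Sections 8.2.1.2 and 8.2.2 disagree on minimum follow-up for ICC. The study is descriptive, so no test or sample size is affected.

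**What to change.** In Section 8.7 (and the SAP), report duration of use as Kaplan-Meier time to discontinuation, by registry. Give the median where reached and persistence at fixed times such as 6, 12 and 24 months. Censor at study end or registry exit, and state how deaths are handled. Keep crude exposure time if wanted, labelled as observed time to the data cut and shown with the number still on treatment. Restricting the summary to patients who stopped is no remedy: in the final-cut scenarios above, their median is 7.7 or 10.2 months against a true 12 or 24.

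Secondary changes:
- Add person-time rates or cumulative incidence for the follow-up events.
- Limit the Week-12 lipid proportion to patients on treatment and observable through the test window.
- Reconcile the ICC 12-week minimum in Section 8.2.1.2 with the absence of any minimum in Section 8.2.2.

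Table 5 lists the discontinuation date as available in all three registries, so the main change needs no new data. The cost is Protocol and SAP wording, routine programming, a somewhat smaller lipid denominator, and a median that may not be reached at the interim.

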## 8.7.1. Missing Values

#### 8.7.1.1. ENEIDA (ES)

No imputation for missing data is done at ENEIDA. In most instances, absence of information for a predefined variable is taken as evidence of absence of the condition, treatment, etc. coded by the variable. For variables with true missingness such as age or sex, missing values will be quantified and accounted for as described in the SAP.

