## 5. MILESTONES

The milestones for the study are presented in Table 2.

Each registry will be deemed to start data collection after the European Commission's (EC) final decision on the Article 20 for Janus kinase inhibitors (JAKi's) (i.e. 10 March 2023; for details, see Section 6) and identification of the first eligible filgotinib patient in the registry.

An interim study report will be provided with data including 24 months of data collection following the study start date; preparation of the interim report will take approximately 9 months. A full analysis will be performed with data including 48 months of data collection; the analyses and drafting of the full report will take approximately 12 months.

*Note*: SWIBREG will require additional time for linkage data to be available. Thus, the consolidated reports will be created once the last registry has provided its results.

The overall study period will therefore account for the timing of the start of the study, the data collection periods (including chart abstraction), data linkage, data management, data analysis, and submission of the consolidated interim and final report.

Milestone	Planned Date
Protocol submission (first version)	Within 18 months after European Commission (EC) approval of filgotinib for the treatment of UC (by 12- May-2023 at the latest)
Start of data collection	With the first patient identified per register after the EC decision date on Article 20 on JAKi's (i.e. after 10 March 2023)
End of interim data collection*	Q1 2027
End of data collection*	Q1 2029
Interim report submission (with 2 years of data)	End of interim data collection + 9 months (Q4 2027)
Registration in the EU PAS register	Within 4 months after protocol approval
Final study report submission (with 4 years of data)	End of data collection + 12 months (Q1 2030)

EU = European Union; PAS = post-authorization study; UC = ulcerative colitis

\* corresponds to the date at which the analytical dataset to perform the statistical analyses is completely available (this would be after chart abstraction in ENEIDA [won't be done for the interim report] and data linkage across the Swedish registers [usually linked data for a calendar year become available approximately 13 months after year-end, i.e. in January the year after next])

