## 8.4.1. ENEIDA (ES)

#### 8.4.1.1. Study Main Data Source: the ENEIDA Registry

ENEIDA is a large, prospectively maintained registry of patients with IBD in Spain established in 2005 (Zabana et al., 2020). It is conducted under the auspices of a national scientific society devoted to the study of IBD (the Grupo Español de Trabajo en Enfermedad de Crohn y Colitis Ulcerosa [Spanish Working Group on Crohn's disease and Ulcerative Colitis] GETECCU). Data in the ENEIDA registry come from a network of more than 90 academic and community gastroenterology practices across Spain that have an interest in IBD. As of February 2023, the registry's entire census of patients with UC was 37865, of which >30000 were on active follow-up. Participation in the registry is voluntary for both physicians and patients, and physicians who contribute data to ENEIDA receive no payment for this registry work. The ENEIDA registry is stored in a password-protected MySQL database that is maintained in a secure server facility and managed by dedicated data managers. The investigator or a qualified designee is responsible for verifying the accuracy of patient data as data are entered into the ENEIDA registry.

Participating sites enter data into an electronic case report form (eCRF), which is immediately uploaded in the central ENEIDA registry. Automated data in ENEIDA comprise a predefined set of clinical variables. The registry mandates completion of a limited number of fields on the eCRF, while completion of other fields is optional.

The general organization of data sources, research team, and the flow of information for the study is presented in Figure 1.

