## 8.7.1.2. ICC (NL)

If data are missing, patients are calculated as nonresponders. However, since there is prospective follow-up and centers are alerted if a visit is in the near future, missing data is limited. ICC does not use imputation for missing values.

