# 9.3. Informed Consent

### 9.3.1. ENEIDA (ES)

This non-interventional study will involve no administration of any therapeutic agent according to the study protocol; patients in ENEIDA are treated in the setting of usual clinical care. Patients whose data are included in ENEIDA previously consented to have their health information included in this database.

For the current study, some of the variables of interest extend beyond the field of UC and are not routinely collected in ENEIDA. As a consequence, a new IC will need to be obtained for this PASS for all patients that participate in the chart abstraction component of the study. If necessary, because of low enrolment in the chart abstraction component, patients for whom an IC cannot be obtained may still participate in the study addressing only those objectives that can be assessed using data collected in the registry.

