Dx date of viral hepatitis	Inconsistently (might be in medical report)	yes	yes (NPR)
Herpes zoster (HZ)	yes (if not available, might be in medical report)	yes	yes (NPR)
Dx date of HZ	Inconsistently (might be in medical report)	yes	yes (NPR)
Screening for TB	yes	no	yes (SmiNet)
Date of screening for TB	yes (possibly in ENEIDA or medical history)	no	yes (SmiNet)
Screening for HZ	yes	no	no
Date of screening for HZ	yes (possibly in ENEIDA or medical history)	no	no
Screening for viral hepatitis	yes	yes	no
Date of screening for viral hepatitis	yes	yes	no
SmPC section 4.4: Special warnings and precautions for use: Haematological abnormalities			
Laboratory measurement of ANC	no (might be in medical report)	no (only total leucocyte count, but it can be added)	yes (currently for <20%)
Date of measurement	no (might be in medical report)	yes (leucocyte count at baseline [week 0])	yes (currently for <20%)
Laboratory measurement of ALC	no (might be in medical report)	no (only total leucocyte count, but it can be added)	yes (currently for <20%)
Date of measurement	no (might be in medical report)		yes (currently for <20%)

Variable	Availability in individual registries yes/no (additional comments)		
	ENEIDA (ES)	ICC (NL)	SWIBREG (SE)
Laboratory measurement of Hb	no (might be in medical report)	yes	yes (currently for <20%)
Date of measurement	no (might be in medical report)	yes	yes (currently for <20%)
SmPC section 4.4: Special warnings and precautions for use: Vaccinations			
Use of live, attenuated vaccines	yes (if not available, might be in medical report)	no (but can be added)	no
Date of vaccine administration	yes		no
HZ vaccination	yes (if not available, might be in medical report)	no (but can be added)	no
Date of vaccine administration	yes		no
SmPC section 4.4: Special warnings and precautions for use: Venous thromboembolism (VTE)			
(Age 65+)	yes	yes	yes
Long-time smoking (current or past) for > 10 years	yes (if not available, might be in medical report)	no (but can be added)	yes (SWIBREG, but suboptimal coverage)
Hx of atherosclerotic CVD	no (might be in medical report)	yes (as part of medical history/comorbidity)	yes (NPR)
Angina	no (might be in medical report)	yes (as part of medical history/comorbidity)	yes (NPR)
Coronary heart disease	no (might be in medical report)	yes (as part of medical history/comorbidity)	yes (NPR)

Variable	Availability in individual registries yes/no (additional comments)		
	ENEIDA (ES)	ICC (NL)	SWIBREG (SE)

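### Section 8.7 and the ENEIDA and ICC missing-data rules are not reconciled; in ENEIDA data without chart abstraction, reading a blank as absence understates contraindications, risk factors and screening

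*Protocol*

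**What the plan says.** Section 8.7 sets a study-wide rule for categorical outcomes: "Counts for missing values will be also tabulated but missing values will not be considered in the percentages". The registry subsections then differ.

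- **ENEIDA (8.7.1.1):** "In most instances, absence of information for a predefined variable is taken as evidence of absence of the condition, treatment, etc". Only variables such as age or sex are treated as truly missing, and their handling is left to the SAP.
- **ICC (8.7.1.2):** "If data are missing, patients are calculated as nonresponders". Like the ENEIDA subsection, it also says that no imputation is done.
- **SWIBREG (8.7.1.3):** no imputation, and missing data are described. This fits Section 8.7. It adds that missing baseline values are expected to be rare.

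On the meaning of a blank in ENEIDA, Section 8.4.1.1 says that a limited number of fields are mandatory, "while completion of other fields is optional". The end-of-data-collection footnote in Section 5 reads: "this would be after chart abstraction in ENEIDA [won't be done for the interim report". Section 9.3.1 adds that, if enrolment in chart abstraction is low, "patients for whom an IC cannot be obtained may still participate in the study addressing only those objectives" which registry data can address.

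**The concern.** The main outputs are proportions of patients with a contraindication, a risk factor or a screening or laboratory test. Each depends on what is done with a blank, and the protocol gives three answers. A difference between registries could then come from the coding rule and not from prescribing.

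The ENEIDA rule matters most. By the protocol's own account, a blank there is weak evidence of absence. The critical variables monitored for completeness (Section 8.4.1.2) cover demographics, UC diagnosis and location, immunosuppressive and advanced therapy, and surgery. They do not include TB, serious infection, pregnancy, diabetes, hypertension, malignancy or previous VTE. Table 5 lists each of these as available in ENEIDA, but possibly only in the medical report. Where charts are not read, an unrecorded contraindication is counted as compliant prescribing, and the risk minimization measures look effective because data are absent.

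**Working it through.** **The plan's own figures.** Section 8.5 uses a 10% proportion in 300 patients. SE = √(0.10 × 0.90 / 300) = 1.73%, and 10% ± 1.96 × 1.73% gives 6.6% to 13.4%, as stated. Its rule of 3 gives 3 / 0.01 = 300 patients for a 1% contraindication; exactly, 1 − 0.99^300 = 95.1%. Both reproduce.

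**The rules on the same data.** Let p be the true proportion and m the fraction missing, unrelated to true status. The documents give no m for the ENEIDA fields, so m is assumed and ranged.

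- Blank = no (8.7.1.1): p(1 − m)
- Missing excluded (8.7): p, with n(1 − m) patients
- Missing = unfavourable (one possible reading of 8.7.1.2): p(1 − m) + m

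For a risk factor or contraindication with p = 10% and n = 300 (95% CI in brackets):

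| m (assumed) | Blank = no | Excluded | Missing = unfavourable |
|---|---|---|---|
| 5% | 9.5% (6.2 to 12.8) | 10.0% (6.5 to 13.5) | 14.5% |
| 20% | 8.0% (4.9 to 11.1) | 10.0% (6.2 to 13.8) | 28.0% |
| 30% | 7.0% (4.1 to 9.9) | 10.0% (5.9 to 14.1) | 37.0% |
| 50% | 5.0% (2.5 to 7.5) | 10.0% (5.2 to 14.8) | 55.0% |

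In the rows for 30% and 50% missing, the blank = no interval no longer contains the true 10%.

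**Detection.** Under blank = no, the chance of at least one recorded case of a 1% contraindication in 300 patients is 1 − (1 − 0.01(1 − m))^300. At m = 20% this is 1 − 0.992^300 = 91.0%; at m = 50% it is 1 − 0.995^300 = 77.8%. The planning value is 95.1%.

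**Screening.** Suppose a screen is truly done in 80% of patients (assumed). Blank = not done gives 80% × 0.8 = 64% at m = 20% and 80% × 0.5 = 40% at m = 50%. The same ENEIDA rule that flatters adherence for conditions worsens it here. ENEIDA lists TB, herpes zoster and viral hepatitis screening, so this case arises.

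**ICC.** Response appears neither in the objectives (Section 7) nor in the variables (Sections 8.3.1 and 8.3.2). Nonresponder therefore maps to no value of any adherence measure.

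**SWIBREG.** Section 8.7.1.3 expects missing baseline values to be rare. Table 5 gives about 57% coverage for long-time smoking, so about 100 − 57 = 43% missing, and under 20% for ANC, ALC and Hb, so more than 80% missing.

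**The case against.** Sections 8.7 and 8.7.1.1 can be read in sequence: the ENEIDA rule defines what counts as missing, and Section 8.7 removes what remains. This is a fair reading. It removes the formal contradiction but not the misclassification, and the missing counts promised in Section 8.7 would then not show the blanks already coded as no.

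Section 8.6.1 plans chart review for all filgotinib patients found in the automated data, and patients without the new consent are kept only if enrolment is low. Section 8.1 discloses that the interim report is limited to registry data, and Section 8.9 acknowledges heterogeneity between registries. These points confine the harm largely to the interim report and to unabstracted patients. They do not say that the resulting proportions are lower bounds.

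The protocol says: "This is a descriptive study without prespecified hypotheses". That lowers the stakes for inference, but the descriptive proportions are the study's product. Section 8.7 also promises a harmonized SAP, which may resolve the conflict. The rules at issue are nevertheless stated outright in the protocol; ENEIDA defers only its truly missing variables.

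A reader might infer three stronger claims that the documents do not support:

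- **Each registry has its own direction of bias.** The direction follows the variable, and Section 8.7 is study-wide. Exclusion is unbiased if values are missing at random.
- **ICC counts missing as non-adherent.** Nothing equates nonresponder with non-adherent, so no direction can be derived.
- **Section 8.7 makes test indicators 100% by construction.** That follows only if a missing result is a missing value of the test-done indicator. For lipids, Section 8.7 speaks of the proportion of patients who have a test, so no recorded test may simply mean no.

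**Conclusion.** The point holds in this form: the three rules are not reconciled, they give different percentages from the same data, and the direction of the error depends on the variable. The clear harm is in ENEIDA data without chart abstraction. The ICC sentence is undefined for this study rather than demonstrably biasing, and the SWIBREG statement conflicts with Table 5.

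The size depends on the missing fraction, which is assumed. At 20% and 50% missing, a true 10% becomes 8% and 5%, and detection of a 1% contraindication in 300 patients becomes 91% and 78%. For blank = no, what counts is the fraction of true positives left blank. If sites record positives more completely than negatives, the understatement is smaller than an overall blank rate suggests. The calculation also takes recorded positives as correct.

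**What to change.** 1. **Conditions in unabstracted ENEIDA data.** Tabulate recorded yes, recorded no and not recorded separately. Report the proportion over all patients, labelled as a lower bound. In the final report, make the abstracted-chart proportion the main estimate. Do not use answered fields alone as the denominator where sites enter only positives, because the proportion would then tend to 100%.
2. **Test-done indicators.** State that the denominator is all patients on treatment in the window. Report the item as not assessable where the registry does not routinely capture the test, for example ANC, ALC and Hb in SWIBREG.
3. **Registry text.** Delete the ICC nonresponder sentence and apply Section 8.7. Correct the SWIBREG statement that missing baseline values are expected to be rare so that it agrees with Table 5.

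The cost is protocol wording and extra table rows. Some cells become lower bounds or not assessable.
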